- The synopsis has been simplified to align with Clinical Trials Regulation and other guidelines (Section 1.1).
- The note for a post-exposure prophylaxis (PEP) study has been removed as the potential PEP design (where the participants with influenza in this study may serve as the index patients for a PEP study) is no longer planned to be related with the current study (Sections 1.1 and 2.1).
- The schedule of activities has been amended to improve the clarity, consistency, and order of footnotes (Section 1.3, Table 1).
- The information about Cobas® essays for SARS-CoV-2 and influenza A/B testing has been removed due to its non-availability in China (Section 1.3, Table 1; Sections 5.1 and 8.10.1)
- [REDACTED]
- The regulatory approval status for baloxavir marboxil in China has been updated (Section 2.2).
- Additional descriptions about the planned proportions of 1–<5 years old and 5–<12 years old patients have been added (Section 4.1 and 9.1.1).
- Participant's body weight at screening for oseltamivir dosage has been updated to align with the prescribing information (Section 6.1.2, Table 7).
- Two stratification factors (age group and high risk factors for influenza complications) have been added for randomization to ensure the target 2:1 allocation ratio within different groups (Section 6.3).
- Prohibited therapy has been updated to include traditional Chinese medicines with antiviral effects (Section 6.8.4).
- It has been made explicit that expedited safety reports are notified to regulatory authorities using applicable systems (Section 8.3.4).
- A statement has been added to allow for potential increase of sample size to ensure an adequate number of a specific group of patients including patients with high risk

factors for influenza complications and patients with positive result for influenza using PCR (Section 9.1.1).

- A statement has been added to enable potential subgroup analyses (Section 9.3.1).
- A description of the technical and organizational security measures taken to protect personal data has been added to align with Roche practices (Section A1–4).
- Due to certain local requirements and an alignment of Sponsor process, it has been clarified that summaries of clinical study results may be available in health authority databases for public access in addition to redacted Clinical Study Reports (Section A1–6).
- A list of high risk factors for influenza complications has been added to define the high risk population (Appendix 8).

Please retain the signed original of this form for your study files. Please return a copy of the signed form as instructed by your local study monitor.

1. **PROTOCOL SUMMARY**

1.1 **SYNOPSIS**

PROTOCOL TITLE: A PHASE *III*, RANDOMIZED, OPEN-LABEL, ACTIVE-CONTROLLED STUDY TO ASSESS THE SAFETY, PHARMACOKINETICS AND EFFICACY OF BALOXAVIR MARBOXIL IN CHINESE PEDIATRIC PATIENTS 1 TO < 12 YEARS OF AGE WITH INFLUENZA SYMPTOMS

REGULATORY AGENCY IDENTIFIER NUMBERS: IND Number: Not applicable
EudraCT Number: Not applicable
EU Trial Number: Not applicable
NCT Number: Not applicable

STUDY RATIONALE

The objective of this study is to evaluate the safety, pharmacokinetics, and efficacy of baloxavir marboxil in Chinese pediatric participants aged 1 to < 12 years with influenza symptoms.

OBJECTIVES AND ENDPOINTS

This study will evaluate the safety, pharmacokinetics, and efficacy of baloxavir marboxil in Chinese pediatric participants aged 1 to < 12 years with influenza symptoms. The table below presents the primary and secondary objectives for the study expressed with use of the estimand framework in accordance with the International Council for Harmonisation (ICH) E9(R1) statistical principles for clinical trials.

| Safety (Primary) Objective | Estimand Definition |
|--|--|
| 
To describe the safety of a single dose of baloxavir marboxil compared with 5 days of oseltamivir administered BID in Chinese pediatric participants | 
Population: All participants aged 1 to < 12 years with influenza symptoms who received at least 1 dose of study treatmentEndpoint:
Incidence, severity, and timing of adverse events, serious adverse events, with severity determined according to NCI CTCAE v5Change from baseline in vital sign measurementsChange from baseline in clinical laboratory test resultsTreatment:
Experiment arm: baloxavir marboxil single doseControl arm: oseltamivir 5 days BIDIntercurrent events and handling strategies
Treatment discontinuation: treatment policy strategyRescue medication: treatment policy strategy |

| Safety (Primary) Objective | Estimand Definition |
|---|--|
| | 
 Population-level summary: No formal statistical testing will be conducted. Analyses will be descriptive. 
 Incidence of adverse events, serious adverse events by System Organ Class, by Preferred Term and by worst severity Change from baseline summaries will be presented overall and by treatment with use of descriptive statistics, including means, standard deviations, medians, and ranges for continuous variables |
| Efficacy (Secondary) Objective | Estimand Definition |
| 
 To describe the clinical efficacy of baloxavir marboxil compared with oseltamivir in Chinese pediatric participants | 
 Population: All participants aged 1 to < 12 years with influenza symptoms who received at least 1 dose of study treatment who have had a laboratory confirmation of influenza infection (PCR result) from any swab sample collected at baseline or during the study Endpoints: 
 Time to alleviation of influenza signs and symptoms, defined as the length of time taken from the start of treatment to the point at which all of the following criteria are met and remain so for at least 21.5 hours: 
 A score of 0 (no problem) or 1 (minor problem) for cough and nasal symptoms (Items 14 and 15 of the CARIFS) A "yes" response to the following question on the CARIFS: "Since the last assessment has the subject been able to return to day care/school (if applicable), or resume his or her normal daily activity in the same way as performed prior to developing the flu?" (if possible) Return to afebrile state (tympanic temperature $\leq 37.2^{\circ}\text{C}$) Duration of fever (time to return to afebrile state [tympanic temperature $\leq 37.2^{\circ}\text{C}$] and remaining so for at least 21.5 hours) Duration of symptoms (alleviation of all symptoms as defined by a score of 0 [no problem] or 1 [minor problem] and remaining so for at least 21.5 hours, for all 18 symptoms specified in the CARIFS questionnaire) Time to return to normal health and activity based on the CARIFS questionnaire Frequency of influenza-related complications (death, hospitalization, radiologically confirmed pneumonia, bronchitis, sinusitis, otitis media, encephalitis/encephalopathy, febrile seizures, myositis) |

| Efficacy (Secondary) Objective | Estimand Definition |
|--|--|
| | 
 – Proportion of participants requiring antibiotics for influenza related complications • Treatment: 
 – Experiment arm: baloxavir marboxil single dose – Control arm: oseltamivir 5 days BID • Intercurrent events and handling strategies 
 – Treatment discontinuation: treatment policy strategy with use of appropriate summary statistics – Rescue medication: treatment policy strategy with use of appropriate summary statistics • Population-level summary: 
No formal statistical testing will be conducted. Analyses will be descriptive.
 
Time to event endpoints and duration endpoints will be summarized with use of Kaplan Meier plots and median survival time for each treatment arm.
 |
| Virology (Secondary) Objective | Estimand Definition |
| 
 • To evaluate the virological activity of baloxavir marboxil compared with oseltamivir in Chinese pediatric participants | 
 • Population: All participants aged 1 to < 12 years with influenza symptoms who received at least 1 dose of study treatment who have had a laboratory confirmation of influenza infection (PCR result) from any swab sample collected at baseline or during the study • Endpoints: 
 – Time to cessation of viral shedding by virus titer and by RT-PCR with use of samples from respiratory swabs – Change from baseline in influenza virus titer and in the amount of virus RNA (RT-PCR) at each timepoint with use of samples from respiratory swabs – Proportion of participants with positive influenza virus titer and proportion of participants positive by RT-PCR at each timepoint with use of samples from respiratory swabs – Area under the curve in virus titer and in the amount of virus RNA (RT-PCR) with use of samples from respiratory swabs • Treatment: 
 – Experiment arm: baloxavir marboxil single dose – Control arm: oseltamivir 5 days BID • Intercurrent events and handling strategies 
 – Treatment discontinuation: treatment policy strategy with use of appropriate summary statistics – Rescue medication: treatment policy strategy with use of appropriate summary statistics |

| Virology (Secondary) Objective | Estimand Definition |
|---------------------------------------|--|
| • | 
 Population-level summary: Summaries will be presented overall and by treatment with use of descriptive statistics, including means, standard deviations, medians, and ranges for continuous variables and proportions for categorical variables. Time to event endpoints will be summarized with use of Kaplan Meier plots and median survival time. |

BID = twice a day; CARIFS = Canadian Acute Respiratory Illness and Flu Scale;
NCI CTCAE = National Cancer Institute Common Terminology Criteria for Adverse Events;
PCR = polymerase chain reaction; RT-PCR = reverse transcriptase polymerase chain reaction.

Other Secondary Objectives and Endpoints

| Pharmacokinetic (Secondary) Objective | Corresponding Endpoints |
|--|---|
| 
 To describe the PK of baloxavir after single-dose administration of baloxavir marboxil in Chinese pediatric participants | 
 Plasma concentrations of S-033447 (active metabolite) will be summarized by time (C_{24} and C_{72}) and body weight Population PK model derived parameters (e.g., AUC_{inf}, C_{max}, T_{max}, $t_{1/2}$) (modeling report) |
| Virology (Secondary) Objective | Corresponding Endpoints |
| 
 To evaluate the polymorphic and treatment-emergent amino acid substitutions in the PA gene and drug susceptibility in participants with evaluable virus in Chinese pediatric participants | 
 Polymorphic and treatment-emergent amino acid substitutions in the PA gene Drug susceptibility in participants with evaluable virus |
| Palatability (Secondary) Objective | Corresponding Endpoint |
| 
 To evaluate the palatability of the oral suspension | 
 Proportion of participants reporting each palatability and acceptability response |

AUC_{inf} = area under the concentration–time curve extrapolated to infinity; C_{24} = concentration at 24 hours postdose; C_{72} = concentration at 72 hours postdose; C_{max} = maximum observed concentration; PK = pharmacokinetic; $t_{1/2}$ = elimination half-life; T_{max} = time of maximum observed concentration.

OVERALL DESIGN AND STUDY POPULATION

This is a multicenter, randomized, open-label, active-controlled (i.e., oseltamivir) study to assess the safety, pharmacokinetics, and efficacy of baloxavir marboxil compared with oseltamivir in Chinese pediatric participants aged 1 to < 12 years with influenza symptoms within 48 hours of symptom onset.

Several key aspects of the study design and study population are summarized below.

| | | | |
|------------------------------|--------------------------------|---|----------------------------------|
| Phase: | Phase III | Population Type: | Pediatric patients |
| Control Method: | Active comparator | Population Diagnosis or Condition: | Influenza |
| Interventional Model: | Parallel group | Population Age: | 1–<12 years |
| Test Product: | Baloxavir marboxil (RO7191686) | Site Distribution: | Multi-site in China |
| Active Comparator: | Oseltamivir | Study Treatment Assignment Method: | Randomization and stratification |
| Number of Arms: | 2 | Number of Participants to Be Enrolled: | Approximately 100 |

STUDY TREATMENT

The investigational medicinal products (IMPs) for this study are baloxavir marboxil *and* oseltamivir. Baloxavir marboxil is the test product. Oseltamivir is an active control.

Participants will be screened and randomized on Day 1 and assigned in a 2:1 ratio to receive a single oral dose of baloxavir marboxil based on body weight (2 mg/kg for participants weighing <20 kg or 40 mg for participants weighing ≥20 kg to <80 kg or 80 mg for those weighing ≥80kg)/[REDACTED] for oral suspension reconstituted with water by site staff or oseltamivir (twice a day dose based on body weight) for 5 days.

DURATION OF PARTICIPATION

[figure not shown]
The study consists of two periods: a 5-day treatment period (mandatory visits on Days 1, 2, and 4) and a 24-day follow-up period (mandatory visits on Days 6, 10, and 29). Therefore, the total study duration for each participant will be 29 days.

COMMITTEES

| | |
|--------------------------------|----------------|
| Independent Committees: | Not applicable |
| Other Committees: | Not applicable |

1.2 STUDY SCHEMA

Figure 1 Study Schema

BID = twice a day.

1.3 SCHEDULE OF ACTIVITIES AND SAMPLE COLLECTION SCHEDULE

Table 1 Schedule of Activities

| Day | Protocol Reference | Day 1 ^a | | Day 2 | Day 3 | Day 4 | Day 5 | Day 6 | Day 10 | Day 15 | Day 29/ET |
|---|-----------------------|------------------------|------------------|----------------|--------------------|----------------|-------|----------------|----------------|--------------------|-------------------|
| Visits | | Screening (Predose) | V1 (Postdose) | V2 | Op V1 ^b | V3 | | V4 | V5 | Op V2 ^b | V6 |
| Visits window (days) | | 0 (–1) | –1 | | | +1 | | –1, +1 | –2, +2 | –3, +3 | ± 3 |
| Visit | | x | | x ^c | x ^c | x ^c | | x ^c | x ^c | x ^c | x ^{c, d} |
| Informed consent | 8 | x | | | | | | | | | |
| Local influenza test | 8.10.1 | x | | | | | | | | | |
| Local SARS-Cov-2 test ^e | 8.10.1 | x | | | | | | | | | |
| Inclusion/exclusion criteria | 5.1 5.2 | x | | | | | | | | | |
| Demographics | 8 | x | | | | | | | | | |
| Medical history | 8 | x | | | | | | | | | |
| Influenza vaccination history | 8 | x | | | | | | | | | |
| Randomization | 4.1 | x | | | | | | | | | |
| Baloxavir marboxil administration | 6.1.1 | x | | | | | | | | | |
| Oseltamivir BID administration ^f | 6.1.2 | x | | x | x | x | x | | | | |
| Palatability assessment | 8.11 Appendix 6 | | x ^g | | | | | | | | |

Table 1 Schedule of Activities (cont.)

| Day | | Protocol Reference | Day 1 ^a | | Day 2 | Day 3 | Day 4 | Day 5 | Day 6 | Day 10 | Day 15 | Day 29/ET |
|--|---|--------------------------|---------------------|--|------------------|--------------------|--------------------------|-------|----------------|----------------|--------------------|-------------------|
| Visits | | | Screening (Predose) | V1 (Postdose) | V2 | Op V1 ^b | V3 | | V4 | V5 | Op V2 ^b | V6 |
| Visits window (days) | | | 0 (–1) | –1 | | | +1 | | –1, +1 | –2, +2 | –3, +3 | ±3 |
| Visit | | | x | | x ^c | x ^c | x ^c | | x ^c | x ^c | x ^c | x ^{c, d} |
| Participant diary | Body temperature ^h | 4.1 8.2.2 | | x ⁱ (4 × daily) | | | x (2 × daily till Day 9) | | | x (once daily) | | |
| | CARIFS symptoms assessment ^j | 4.1 8.1.1.1 A5–1.1 | | x ⁱ (twice a day till Day 9) | | | | | | x (once daily) | | |
| Physical examination ^k | | 8.2.1 | x | | x | (x) | x | | x | x | (x ^l) | x |
| Vital signs | | 8.2.2 | x | | x | (x) | x | | x | x | (x ^l) | x ^m |
| Concomitant therapies assessment | | 6.8 | x | | x | (x) | x | | x | x | (x ^l) | x |
| Clinical laboratory tests | | 8.2.3 | | x | | | | | x | | (x ^l) | (x ^l) |
| Respiratory samples (central virology test) ⁿ | | 8.10 | x | | x | | x | | x | x | (x ^l) | (x ^l) |
| PK samples ^o | | 8.4 | | x ^p | (x) ^p | | (x) ^p | | x | | | |
| Adverse event assessment ^q | | 8.3 Appendix 3 | | x | x | (x) | x | | x | x | (x ^l) | x |

Table 1 Schedule of Activities (cont.)

BID = twice a day; CARIFS = Canadian Acute Respiratory Illness and Flu Scale; ET = Early termination; Op = optional; PCR = polymerase chain reaction; PK = pharmacokinetic; SARS-CoV-2 = severe acute respiratory syndrome–coronavirus 2; V = visit.

- ^a Informed consent/assent and screening in Index Patients can be performed on the day before Day 1.
- ^b OpV1 and OpV2 are optional visits to be performed at the discretion of the investigator or parent/caregiver, e.g., in the event of persistent influenza symptoms.
- ^c The visit may be a home visit performed by a mobile nursing professional for appropriate sites.
- ^d Can be performed remotely.
- ^e Participants will test for SARS-CoV-2 with point-of-care/local laboratory *methods*. Only participants testing PCR (–) or antigen (–) for SARS-CoV-2 will be enrolled into the study.
- ^f Oseltamivir will be given orally, 12 hours apart. If the first dose is taken after 4 p.m. (16:00 hours) on Day 1, the next dose will be taken in the morning of Day 2. For these participants, the tenth dose will be taken on the morning of study Day 6. *If the first dose is taken prior to 4 pm (16:00 hours) on Day 1, the next dose should be taken in the evening of the same day (i.e., prior to midnight on the same calendar day with a minimum of 7 hours between doses). For these participants, the tenth dose will be taken in the evening of study Day 5.*
- ^g The palatability questionnaire ([Appendix 6](#)) should be completed as soon as possible after swallowing the baloxavir marboxil drug solution on Day 1. The questionnaire will be completed for pediatric participants receiving baloxavir marboxil only.
- ^h The parent/caregiver will assess and record in the participant diary, body temperature (tympanic assessment) 4 times daily (morning, noon, evening, and bedtime) from Days 1–3; twice daily (morning and evening) on Days 4–9; once daily on Days 10–15. The results will be recorded in the participant diary.
- ⁱ On Day 1, symptom and temperature assessments for the participant diary should only be completed and filled out for the postdose time window(s).
- ^j The parent/caregiver will complete the CARIFS questionnaire twice a day (morning and evening) on Days 1–9 and then once a day on Days 10–15. The results will be recorded in the participant diary.
- ^k A complete physical examination will be conducted at screening. Limited, symptom-directed physical examinations will be performed postdose. Height and body weight will be measured at screening only.
- ^l Conduct assessment if the investigator determines that influenza symptoms or viral shedding are persisting or at the investigator's discretion.
- ^m Vital signs will be recorded if abnormal physical examination findings or adverse events are recorded since the last visit or at the investigator's discretion on Day 29.
- ⁿ *Respiratory samples will be collected using nasopharyngeal or nasal swabs. At each swab timepoint, a virology test will be performed by the central laboratory.*
- ^o PK samples will be collected in baloxavir marboxil treated participants and sent to a central laboratory.

Table 1 Schedule of Activities (cont.)

-
- ^p PK samples will be collected at Day 1 (1 sample between 0.5 and 2 hours postdose). Participants will be assigned to have either the Day 2 (24 hours postdose) or the Day 4 sample (72 hours postdose). Only 1 sample from Days 6–10 is required and can be collected at either Visit 4 or Visit 5.
- ^q After informed consent has been obtained but prior to initiation of study treatment, only serious adverse events caused by a protocol-mandated intervention should be reported. After initiation of study treatment, all adverse events will be reported until 28 days after the first dose of study treatment. After this period, the Sponsor should be notified if the investigator becomes aware of any serious adverse event that is believed to be related to prior exposure to study drug (see [Appendix 3](#)).

Table 2 Schedule of Pharmacokinetic Samples

| Visit Day | Timepoint | Sample Type |
|--------------------|---|--------------------|
| Day 1 | One sample between 0.5 and 2 hours postdose | Drug PK (plasma) |
| Day 2 ^a | 24 hours postdose | Drug PK (plasma) |
| Day 4 ^a | 72 hours postdose | Drug PK (plasma) |
| Days 6–10 | Only 1 sample is to be collected at visit Day 6 or Day 10 | Drug PK (plasma) |

PK=pharmacokinetic.

^a Participants will be assigned to have either the Day 2 or Day 4 sample taken.

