8.2.3 Clinical Safety Laboratory Tests

See [Appendix 2](#) for the list of clinical laboratory tests to be performed and to the schedule of activities (see Section [1.3](#)) for the timing and frequency.

The investigator must review the laboratory report, document this review, and record any clinically relevant changes occurring during the study in the Adverse Event Case Report Form (CRF, see [Appendix 3](#)).

All laboratory tests with values considered clinically significantly abnormal during participation in the study or within 28 days of the first dose of study treatment should be repeated until the values return to normal or baseline or are considered to be stable and no longer considered clinically significant by the investigator. If such values do not return to normal or baseline within a period of time judged reasonable by the investigator, the etiology should be identified and the Sponsor notified.

If laboratory values from non-protocol-specified laboratory assessments performed at the institution's local laboratory require a change in participant management or are considered clinically significant by the investigator (e.g., serious adverse event or adverse event or dose modification), the results must be recorded on the eCRF.

Sample collection may be performed by an MN professional.

Samples collected for safety laboratory tests will be destroyed no later than the time of completion of the final Clinical Study Report.

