#### **4.2.2.3 Laboratory Data**

For each of the hematological and biochemical test parameters, summary statistics of observed and change from baseline values at each time point will be presented by treatment group for each scheduled time point. For laboratory parameters, post-dose observations on Day 1 will be classed as baseline.

Each observed value will be classified into three categories: Normal (for values within the normal range), High (for values higher than normal) and Low (for values lower than normal). The frequency of each category will be summarized by treatment group for each scheduled time point. Additionally, a shift table will present the changes from baseline at each scheduled time point.

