#### **4.2.2.4 Vital Signs**

Vital signs (pulse rate, respiratory rate, blood pressure) and change from baseline will be summarized by each scheduled time point. Baseline is defined as the last assessment prior to treatment.

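### Late vital signs and laboratory values are collected on condition-related or discretionary triggers, yet the SAP tabulates these primary endpoints at every scheduled time point

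*Protocol*

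**What the plan says.** **Collection of vital signs (Protocol 1.3, Table 1).** They are unconditional at screening and on Days 2, 4, 6 and 10. Days 3 and 15 are optional visits with bracketed assessments. On Day 29 footnote m applies: "Vital signs will be recorded if abnormal physical examination findings or adverse events are recorded since the last visit". The sentence goes on to add discretion: "or adverse events are recorded since the last visit or at the investigator's discretion on Day 29". The Day 29 visit may be remote (footnote d).

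**Collection of laboratory tests.** Table 1 has unconditional tests on Day 1 postdose and on Day 6, none on Day 10, and bracketed tests on Days 15 and 29 under footnote l: "Conduct assessment if the investigator determines that influenza symptoms or viral shedding are persisting or at the investigator's discretion". Separately, Protocol 8.2.3 covers "All laboratory tests with values considered clinically significantly abnormal during participation in the study or within 28 days of the first dose"; these "should be repeated until the values return to normal or baseline" or are judged stable.

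**Analysis.** Change from baseline in vital signs and in laboratory results are both components of the primary safety estimand (SAP Table 1), presented overall and by treatment. SAP 4.2.2.4 states: "Vital signs (pulse rate, respiratory rate, blood pressure) and change from baseline will be summarized by each scheduled time point". SAP 4.2.2.3 gives laboratory summary statistics and Low/Normal/High frequencies by arm at every scheduled time point, then adds: "Additionally, a shift table will present the changes from baseline at each scheduled time point". SAP Table 5 lists Optional Visit 1 (Day 3), Optional Visit 2 (Day 15) and Visit 6 (Day 29) among the time points, and an empty window counts as missing. Nothing restricts the tables to the unconditional visits or marks the late values as selectively collected.

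**The concern.** A by-visit table with arms side by side is normally read as describing the randomised groups at that visit. Here the Day 15 and Day 29 columns would describe children who were measured because of how they were doing, or because the investigator chose to measure them. Children without a value are not missing by accident: whether a value exists depends on the child's course after treatment.

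Two things are at stake. Within an arm, the late mean or abnormal share may not represent the children treated. Between arms, the comparison loses the protection of randomisation, and because the study is open-label, the discretionary route can be used differently in the two arms. The study is descriptive, so these tables are themselves the primary results, and no model or test stands behind them to correct for selection.

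**Working it through.** The plan gives no trigger rate, so it has no figure of its own on this point. Its one sample-size figure, which comes with the arm sizes used below (67 and 33, Protocol 9.1.1), reproduces: 1 − 0.97^67 = 0.870 against the stated 87%. Nothing below depends on it.

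**Step 1. Which columns are complete by design**

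| Day | Vital signs | Laboratory tests | SAP Table 5 window |
|---|---|---|---|
| 1 | all, predose | all, postdose (SAP baseline) | Day 1 |
| 2 | all | none | Day 2 |
| 3, optional | conditional | none | Day 3 |
| 4 | all | none | Day 4 |
| 6 | all | all | Days 5–7 |
| 10 | all | none planned | Days 8–12 |
| 15, optional | conditional (l) | conditional (l) | Days 13–22 |
| 29 | conditional (m) | conditional (l) | Day 23 onward |

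So there are four complete post-baseline time points for vital signs and one for laboratory tests.

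**Step 2. Where repeats land.** SAP 4.1.1 uses measurements falling inside a window for that time point. Read literally, a repeat of an abnormal Day 6 value drawn between Day 8 and Day 12 enters a Visit 5 laboratory column. No test is planned for that visit, so the column would contain only repeats and other unplanned tests. A repeat drawn from Day 13 enters the Day 15 or Day 29 column.

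**Step 3. Effect on a mean.** Let q be the share measured in an arm, and G the mean among measured children minus the mean among unmeasured children. The all-children mean equals the measured mean minus (1 − q) × G, so the table is off by (1 − q) × G. The documents give neither q nor G, so q is assumed over a range:

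| q | Baloxavir, q × 67 | Oseltamivir, q × 33 | Error |
|---|---|---|---|
| 10% | 6.7 | 3.3 | 0.9 G |
| 20% | 13.4 | 6.6 | 0.8 G |
| 30% | 20.1 | 9.9 | 0.7 G |
| 50% | 33.5 | 16.5 | 0.5 G |
| 100% | 67 | 33 | 0 |

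**Step 4. Effect on the comparison.** The error in the between-arm difference is (1 − q₁)G₁ − (1 − q₂)G₂, with 1 and 2 denoting the arms. It cancels if both arms have the same q and the same G. If G is common but 20% are measured in one arm and 30% in the other, it is 0.8 G − 0.7 G = 0.1 G. Nothing in the plan ensures equal q or equal G.

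**Step 5. Effect on an abnormal share (illustration).** Assume a true late share of 3%, every abnormal child tested, and the others tested with probability q. The table then shows 0.03 / (0.03 + 0.97 q):

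- q = 10%: 0.03 / 0.127 = 24%
- q = 20%: 0.03 / 0.224 = 13%
- q = 30%: 0.03 / 0.321 = 9%
- q = 50%: 0.03 / 0.515 = 6%

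Footnote l does not guarantee that every abnormal child is tested, so this shows a mechanism and is not an estimate.

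**The case against.** A good deal can be said on the other side.

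- **Discretion is allowed throughout.** A reader might infer that Day 29 vital signs exist only after an adverse event or abnormal examination. The documents do not say that: footnotes l and m both permit assessment at discretion, and sites could measure every child they see, in which case the error is zero. This stands. But discretion does not make collection systematic, and the plan does not ask for everyone to be measured.
- **An abnormal value is not a Table 1 trigger.** It comes from Protocol 8.2.3, covers clinically significant values only, and governs repeats on no fixed day. This also stands; such repeats reach a visit column only through the SAP windows.
- **Late worsening is not built in.** A reader might infer that the late columns must look worse. Children enter with fever of at least 38°C and the vital-sign baseline is predose, so pulse could fall from baseline even in triggered children. The trigger includes adverse events that have resolved or have nothing to do with pulse or blood pressure, and laboratory repeats continue until values normalise, return to baseline or are stable. The direction is open.
- **Late safety is captured elsewhere.** Adverse events are collected from all children for 28 days after the first dose. Clinically significant new vital-sign findings and clinically relevant laboratory changes are recorded as adverse events and summarised by arm. This limits the harm, but does not make the late columns of the vital-sign and laboratory tables interpretable.
- **The protocol already plans a worst-grade shift table (9.3.2).** It does, but SAP 4.2.2.3 describes only a shift table by time point, although the SAP introduction states that no planned analysis has changed. A worst-grade table is also not free of the problem: children measured more often have more chances to show a worst value.

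**Conclusion.** The point holds as a mismatch between conditional collection and unconditional tabulation of two primary endpoint components. Followed as written, the SAP produces late by-arm columns for a selected subset, which are not a randomised comparison and may be biased.

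The size cannot be stated from the documents. At an assumed 20% measured, about 13 of 67 and 7 of 33 children contribute, and an arm's mean is off by 80% of an unknown gap; over 10% to 50% measured the factor runs from 90% to 50%, and it is zero if all are measured. Any figure in beats per minute or percentage points would rest on an invented gap, so none is claimed.

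The scope is limited. Vital signs through Day 10, the scheduled Day 6 laboratory data and adverse event capture to Day 29 are unaffected. No hypothesis test or power figure changes. The change is worth making before the tables are programmed, because it is cheap and concerns primary results.

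**What to change.** In SAP 4.2.2.3 and 4.2.2.4:

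1. Limit by-visit means, changes from baseline, category frequencies and shifts to the unconditional visits: Days 2, 4, 6 and 10 for vital signs, and Day 6 for laboratory tests.
2. List the Day 3, 15 and 29 values and any unscheduled repeats. Alternatively, show them in a separate table labelled as conditionally collected, with the number measured and the reason for assessment by arm.
3. Restore the Protocol 9.3.2 laboratory shift table of baseline against maximum post-baseline grade. Show children with no post-baseline value as their own category, and note that follow-up is unequal.

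The cost is SAP wording and table shells, with no new assessments. The documents do not say whether the reason for a conditional assessment is recorded. If it is not, it could be derived in part from adverse event, diary and earlier laboratory records, and otherwise reported as unknown. The downside is the loss of stand-alone by-visit late columns for these parameters.
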